### **Consent Process**

The researchers will follow SOP CW AHC 216 Informed Consent Process and Written Documentation of Informed Consent. Also, the researchers will follow SOP CW AHC 249 Remote and Electronic Methods for Conducting Informed Consent in Non-Exempt Research.

**For Patients:** Upon referral for definitive diagnosis based on their cancer screening results, patients will be contacted by a study team member for informed consent for survey completion, interviews and electronic health record access to monitor outcomes. All consent forms will be completed on paper or electronically via REDCap on a tablet device provided by the study team.

**For Stakeholders:** Study team members will contact community stakeholders in person, or via phone or email to re-explain the study and obtain consent. Consent forms may be completed on paper or electronically via REDCap.

**Subjects who are not yet adults (infants, children, teenagers)**  
N/A

**Cognitively Impaired Adults**  
N/A

**Adults Unable to Consent**  
N/A

### **Documentation of Informed Consent Process**

A member of the study team will note the following in the Enrollment Log: the participant's name, phone number, email address (if applicable), the date of screening, the date the informed consent was signed, whether inclusion/exclusion criteria were met (and reason if excluded), screening outcome, completion of study or withdrawal (and reason if withdrawal), and investigator terminated (and reason) if applicable. The Enrollment Log will be saved in the shared Microsoft OneDrive folder.

**Waiver of Written Documentation of Consent or Waiver of Consent  
Waiver of Written documentation of Consent (consent will be obtained but  
signatures will not be required)**

N/A

**Waiver or Alteration of the Consent Process (consent will not be obtained,  
required information will not be disclosed, or the research involves  
deception)**

N/A

**Waiver or Alteration of HIPAA Authorization**

N/A

**Non-English Speaking Subjects**

Check here to confirm you will follow HRP-804 INVESTIGATOR GUIDANCE  
Short Form Consent Process

Consent forms and all study materials will be translated into Spanish for both Spanish-speaking patients and stakeholders.

For patients and stakeholders that speak Spanish as a primary/preferred language, the study team will ensure that a Spanish-speaking research team member is in place to navigate the consent process, study activities, provide directions, and guidance on next steps.

For patients:

Spanish-speaking participants will be included only in surveys that are validated in English and Spanish. Spanish-speaking participants will be eligible for focus groups and interviews with a Spanish-speaking team member.

Those patients who do not speak English or Spanish as a primary language will be consented appropriately using a consent form that is fully translated and provided to the participant as soon as possible. These individuals will be eligible for medical record tracking for follow-up but will not participate in surveys or interviews.

For all non-English speakers, short form consents will be utilized using medical translators until regulatory requirements dictate translation of consent.

**Randomization**

N/A

**Study Visits**

For patients, study visits include:

- Consent and enrollment and at the site of confirmatory diagnostics and/or emergency room or healthcare center

- 1 or more interviews with the research team throughout the study period
- Survey package completion with coordinator at a site of diagnosis or care

Study Visit	1	2	3	4	5	6	7	8
Consent/Enrollment	X							
Baseline Surveys		X						
First Interview			X					
3-Month Surveys				X				
Optional Follow-Up Interviews					X	X	X	X

For stakeholders, study visits include:

- Consent and enrollment
- Ongoing stakeholder meetings throughout the duration of the study up to 12.
- 1 or more interviews with the research team throughout the study period.

Study Visit	1	2	3	4	5	6	7	8	9	10	11	12	13	14	15	16	17	18
Consent/Enrollment	X																	
Stakeholder Meetings		X	X		X	X		X	X		X	X		X	X		X	X
First Interview				X														
Optional Follow-Up Interviews							X			X			X		X			

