### Inclusion Criteria

The inclusion criteria for patients will be the following:

1. Adult aged 18 or older
2. Seeking care at a CRS or emergency department
3. Meets criteria for lung, breast, and/or prostate cancer screening, as outlined below:
  - a. Lung cancer: Adults aged 50 to 80 years who have a 20 pack-year smoking history and currently smoke or have quit within the past 15 years
  - b. Breast cancer: Women aged 40 to 74 years
  - c. Prostate cancer: Men aged 55 to 69 years
4. Receives a positive screening result for lung, breast, and/or prostate cancer at a study site

The inclusion criteria for stakeholders will be the following:

1. Speaks English or Spanish through study interpreters
2. Able to attend 75% or more of scheduled meetings
3. Must be key individuals providing critical services to address food insecurity, employment assistance, government support, mental and physical health, and health education within identified Community Resource Spots, emergency departments, and urgent care centers.

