## Study Duration

The project is projected to begin on August 1, 2025. Study subjects will be enrolled for 9 months. Participants will remain active in the study until they have received a definitive diagnosis and treatment plan or declined further care. The study activities, including data analysis, will be completed within 12 months from the start date.

The implementation plan that details study activities and timelines will be developed according to current best practice for evaluating effectiveness and will be informed by input from the stakeholder group at each site. The implementation plan is as follows:

- Month 1: Finalize key stakeholders at each site and initiate monthly implementation meetings with study team and including stakeholders as needed, collect baseline data and initiate ongoing data gathering (i.e., lung, breast, prostate cancer screening knowledge, attitudes, and practices, cancer screening barriers and facilitators), establish care navigation and communication processes and launch project.
- Month 2: Data collection and monitoring of all sites, implementation meetings.
- Month 3: Data collection and monitoring of all sites, implementation meetings.
- Month 4: Data collection and monitoring, implementation cycle 1 adjustments, stakeholder meetings for data sharing and plans, patient study enrollment.
- Months 5-7: Continue monthly implementation meetings, data collection, study enrollment, data-driven process improvement.
- Month 8: Stakeholder meetings, implementation cycle 2 adjustments.

- Months 9-10: Continue monthly implementation meetings, data collection, study enrollment, process improvement.
- Month 11: Final data collection and analyses.
- Month 12: Final reporting, stakeholder meeting and sustainability plan development.

	FL CANCER FUND PROJECT PERIOD MONTHS											
	1	2	3	4	5	6	7	8	9	10	11	12
Implementation plan finalized	X											
Implementation plan socialized	X											
Stakeholder meeting (x # sites)	SM	SM	SM	SM	SM	SM	SM	SM	SM	SM	SM	SM
Active Implementation period	Zipcode 1											
	MONITORING/ADJUSTMENTS AS NEEDED											
	Zipcodes 2 & 3											
Implementation Iteration cycles				Cycle 1					Cycle 2			
Data collection	BASELINE	X	X	X	X	X	X	X	X	X	X	FINAL
Interview themes + Quantitative data review		X	X	X	X	X	X	X	X	X	X	X
Reporting requirements			PR due			PR due			PR due			FR due

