Medical records will be followed until definitive diagnosis and treatment disposition to track the patients' progress through the cancer care continuum. If diagnosis is negative, then interaction with the medical record ends upon confirmation of negative test. If diagnosis is positive, then the medical record is followed monthly to determine: diagnostic codes, treatment decisions, treatment course, and treatment outcomes. This may include labs, demographics, medication histories, referrals, outpatient visit notes, inpatient progress notes, and imaging.

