### Patient Participants – Quantitative

English-speaking patients will complete a package of surveys regarding health and perceptions of cancer navigators. Patient demographics will be obtained to include age, race, ethnicity, sex and gender, marital status, primary language, birth country, employment, education level, household income, insurance and type, housing/shelter, food, transportation insecurity, and environmental safety.

Patient-reported outcomes will occur at baseline and 3-month follow-up. These outcomes will include the PROMIS Global Health (HR-QoL) scale (Hays et al., 2009) to ascertain health-related quality of life to assess physical, mental, and social health and the Patient Satisfaction with Logistical Aspects of Navigation Scale (PSN-L) (Carle et al., 2014) to assess satisfaction with the navigation program. Additionally, barriers will be measured by the barriers to cancer care assessment used in the NCI Patient Navigation Research Program (Freund et al., 2008).

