### **Data Quality**

Participants will complete all surveys electronically through REDCap, and this data will be exported into an Excel file, limiting the need for transcription and potential errors to occur. Quality of qualitative data will be ensured by checking transcripts against recordings of focus groups and interviews.

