### **Statistical Analysis Plan**

#### **Primary Objective Analysis**

Patient-reported demographic characteristics will be analyzed using descriptive statistics associated with the **Reach** aim. To address the **Effectiveness** aim pre- and post-intervention barriers data and patient-reported outcomes will be analyzed using univariate, bivariate, and repeated measures analyses. Referral data will be

descriptively evaluated based on percent increase/decrease across the intervention. Qualitative data will be analyzed to determine the extent to which the **Adoption** aim was met. Analyses of the fidelity of the intervention, including timeliness and consistency will be documented as part of the **Implementation** aim. Finally, process-level descriptions, including the summation of monthly team meetings and direct communications with the Implementation Scientist of the community-focused multi-disciplinary navigation intervention will be used to assess the **Maintenance** aim.

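### The only survey route the protocol names depends on attending a care site, so the 3-month survey may under-represent patients cleared of cancer and those who decline care

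*Protocol*

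**What the plan says.** Patients enter on a positive screen, before the result is confirmed. The patient criterion under Inclusion Criteria reads "Receives a positive screening result for lung, breast, and/or prostate cancer at a study site". The sample therefore includes people who will later be found not to have cancer.

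Study Visits lists the patient visits, among them "Survey package completion with coordinator at a site of diagnosis or care". Its table has a baseline survey and a 3-month survey, with no distinction by diagnosis. Patient Participants – Quantitative agrees: "Patient-reported outcomes will occur at baseline and 3-month follow-up". Data Quality gives the medium: "Participants will complete all surveys electronically through REDCap". It does not say where the patient is when this happens.

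Three other places bear on who can still be reached at three months:

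- Study Duration: "Participants will remain active in the study until they have received a definitive diagnosis and treatment plan or declined further care".
- Dashboard and Records, after a negative work-up: "If diagnosis is negative, then interaction with the medical record ends upon confirmation of negative test".
- Dashboard and Records, after a positive one: "If diagnosis is positive, then the medical record is followed monthly".

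The 3-month data feed the Effectiveness aim. Under Primary Objective Analysis, pre/post barriers data and "patient-reported outcomes will be analyzed using univariate, bivariate, and repeated measures analyses".

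**The concern.** The one survey route in the text requires the patient to be where diagnosis or care takes place. A patient in treatment will often be there at three months. A patient who has been cleared, or who has turned down further care, has no care reason stated in the protocol to be there.

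Barriers to care and satisfaction with navigation are plausibly related to whether someone is still attending. If so, the missing 3-month surveys would be informative and the change scores would describe a selected group. Patients who decline care matter most here, because the first secondary goal is to compare them with those who accept. No analysis can restore surveys that were never collected, so this has to be settled in the data-collection procedure and cannot wait for an analysis plan.

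**Working it through.** **1. The passages side by side**

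| Question | What the protocol gives |
|---|---|
| Who is due a 3-month survey? | Every patient participant, subject to the language limits (Study Visits; Patient Participants – Quantitative; Non-English Speaking Subjects) |
| Where is it done? | One setting, tied to diagnosis or care, with the coordinator (Study Visits) |
| Is there another route? | None named. Data Quality fixes REDCap as the medium only |
| Are remote options named elsewhere? | Yes: virtual interviews (Patient Participants – Qualitative) and a remote/electronic consent procedure (Consent Process) |
| Who is still active at 3 months? | Not those with a diagnosis and treatment plan, nor those who have declined care (Study Duration). Cleared patients are not mentioned separately |
| What happens to non-completers? | They are asked why; recovering the survey is not mentioned (Data Collection and Follow-up for Withdrawn Subjects) |

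The 3-month survey is thus due from people whom the exit rule has already released, by a route that presumes they attend care.

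**2. Illustration of size**

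The protocol states no figure to reproduce: the patient sample is a convenience sample, with no confirmation rate and no expected completion rate. The only input from the documents is N = 200, the estimated number of subjects at all sites. The rest are assumptions:

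- p = share of enrolled patients with confirmed cancer (0.10, 0.20, 0.40)
- r_c = 3-month completion if cancer is confirmed (0.80)
- r_n = 3-month completion in everyone else (0.60, 0.40, 0.20)

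Completers = N·p·r_c + N·(1 − p)·r_n

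Cancer share among completers: s = p·r_c / [p·r_c + (1 − p)·r_n]

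Worked case, p = 0.10 and r_n = 0.40: 200 × 0.10 × 0.80 = 16; 200 × 0.90 × 0.40 = 72; completers = 88; s = 16/88 = 18.2%.

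| p | r_n = 0.80 (equal) | r_n = 0.60 | r_n = 0.40 | r_n = 0.20 |
|---|---|---|---|---|
| 0.10 | 160; 10% | 124; 12.9% | 88; 18.2% | 52; 30.8% |
| 0.20 | 160; 20% | 128; 25.0% | 96; 33.3% | 64; 50.0% |
| 0.40 | 160; 40% | 136; 47.1% | 112; 57.1% | 88; 72.7% |

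Each cell gives completers, then cancer share.

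**3. What a tilt would do to a mean change**

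Let D be the difference in mean change between confirmed patients and the rest, and suppose loss is random within each group. The completers' mean change then differs from the enrolled mean change by (s − p)·D. For p = 0.10 and r_n = 0.40 that is (0.182 − 0.10)·D = 0.082·D. For p = 0.20 and r_n = 0.20 it is (0.50 − 0.20)·D = 0.30·D. The protocol gives no D. Selective loss within a group, such as decliners among confirmed patients, would come on top and is not captured here.

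**4. Limits of the illustration**

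The survey base will be below 200, because some patients are outside the survey package for language reasons; under the same rates the shares do not change. One rate for everyone without confirmed cancer is a simplification, since those with unfinished work-up may still attend. The direction depends on r_n being below r_c. If the exit rule also cut r_c, say to r_c = r_n = 0.40, there would be 200 × 0.40 = 80 completers and no tilt by diagnosis, but half the completers of the 0.80 case would be lost.

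**The case against.** A reader might infer that surveys must be done on site and that cleared patients have no 3-month visit. The text does not go that far. Study Visits says the visits include this activity, and its table schedules the 3-month survey for all patients. A cleared patient could be asked back, and the settings include emergency departments and community clinics to which this population returns for episodic care. REDCap surveys could also be completed elsewhere, although the protocol does not say so.

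A reader might also infer that the follow-up sample will tilt towards cancer patients. That is a risk and not a finding. Every rate behind it is assumed, and the exit rule under Study Duration threatens the 3-month survey of confirmed patients as well.

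A third tempting inference is that satisfaction scores are inflated because patients answer in front of programme staff. The documents do not support this. Resources Available lists the research coordinator separately from the navigators, no section gives the coordinator a navigation role, and electronic completion is compatible with patients answering by themselves.

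Assisted in-person completion is also defensible in a population with unstable housing and transport. Interviews can be virtual and cover barriers, non-completers are asked for their reasons, and short-term attrition is already a tracked measure.

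These points limit the claim but do not remove it. Interviews do not supply the 3-month scale scores, asking for reasons does not recover a survey, and an incidental return visit cannot be relied on. The protocol names remote options for interviews and consent but none for surveys.

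**Conclusion.** The point holds as a gap with a credible consequence. The only survey route written down depends on presence at a care site, and the exit rule conflicts with a 3-month survey due from everyone. Followed as written, the plan risks under-representing cleared patients and care decliners in the pre/post Effectiveness analysis. This rests on one assumption: that people without a care reason to attend complete the survey less often.

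The size cannot be set from the protocol. Over the assumed grid with unequal completion, the cancer share among completers rises by 2.9 points (12.9% against 10%) to 32.7 points (72.7% against 40%), and completers number 52 to 136 instead of 160. These figures show sensitivity and do not predict the result. The change is a cheap improvement, most useful before 3-month surveys fall due.

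**What to change.** Amend Study Visits along these lines: *The 3-month survey is sought from every survey-eligible participant, whatever the diagnosis or care status. It is completed in person or, failing that, through a REDCap link or by telephone. The mode is recorded.*

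Then:

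- Reconcile Study Duration with this, so that participation runs through the 3-month survey for cleared patients, confirmed patients and decliners alike. Withdrawal of consent stays as it is.
- Make clear in Dashboard and Records that the end of record follow-up after a negative test does not end survey contact.
- Report 3-month response by diagnostic outcome and by acceptance of care.

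The cost is wording, a survey link and some coordinator time. REDCap is already in use, and the Enrollment Log already holds telephone numbers, with email where applicable. The downside is mixed modes of completion, which recording the mode lets the analysis examine.

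This change does not settle the calendar. Study Duration lists enrolment in month 10, and 10 + 3 = 13 lies beyond the 12-month study, so the latest enrolees would still miss the survey unless that too is addressed.

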## Study Duration

The project is projected to begin on August 1, 2025. Study subjects will be enrolled for 9 months. Participants will remain active in the study until they have received a definitive diagnosis and treatment plan or declined further care. The study activities, including data analysis, will be completed within 12 months from the start date.

The implementation plan that details study activities and timelines will be developed according to current best practice for evaluating effectiveness and will be informed by input from the stakeholder group at each site. The implementation plan is as follows:

- Month 1: Finalize key stakeholders at each site and initiate monthly implementation meetings with study team and including stakeholders as needed, collect baseline data and initiate ongoing data gathering (i.e., lung, breast, prostate cancer screening knowledge, attitudes, and practices, cancer screening barriers and facilitators), establish care navigation and communication processes and launch project.
- Month 2: Data collection and monitoring of all sites, implementation meetings.
- Month 3: Data collection and monitoring of all sites, implementation meetings.
- Month 4: Data collection and monitoring, implementation cycle 1 adjustments, stakeholder meetings for data sharing and plans, patient study enrollment.
- Months 5-7: Continue monthly implementation meetings, data collection, study enrollment, data-driven process improvement.
- Month 8: Stakeholder meetings, implementation cycle 2 adjustments.

- Months 9-10: Continue monthly implementation meetings, data collection, study enrollment, process improvement.
- Month 11: Final data collection and analyses.
- Month 12: Final reporting, stakeholder meeting and sustainability plan development.

	FL CANCER FUND PROJECT PERIOD MONTHS											
	1	2	3	4	5	6	7	8	9	10	11	12
Implementation plan finalized	X											
Implementation plan socialized	X											
Stakeholder meeting (x # sites)	SM	SM	SM	SM	SM	SM	SM	SM	SM	SM	SM	SM
Active Implementation period	Zipcode 1											
	MONITORING/ADJUSTMENTS AS NEEDED											
	Zipcodes 2 & 3											
Implementation Iteration cycles				Cycle 1					Cycle 2			
Data collection	BASELINE	X	X	X	X	X	X	X	X	X	X	FINAL
Interview themes + Quantitative data review		X	X	X	X	X	X	X	X	X	X	X
Reporting requirements			PR due			PR due			PR due			FR due

## Materials of Human Origin: Collection, Preparation, Handling and Shipping

N/A

## Study Outcome Measures (Endpoints)

### Dashboard and Records

There will be an information architect on the study team who will build and maintain a dashboard to track the project metrics. These metrics can be categorized into the RE-AIM model dimensions of Reach, Effectiveness, Adoption, Implementation, and Maintenance, which are outlined below.

- **Reach**
  - Percentage and characteristics of patients included or excluded
  - Percentage of patients who receive screening at point of care or referral
  - Characteristics of participants and non-participants
- **Effectiveness**
  - All positive screens referred for confirmatory diagnostics
  - Measure of screening rates with comparison to the goals set forth in Healthy People 2030 (HP2030)
    - Increase the proportion of adults aged 55 to 80 years (30-pack-year smoking history, currently smoking or quit in the past 15 years) who receive a lung cancer screening to meet the HP2030 target of 7.5%
    - Increase the proportion of females aged 40 to 74 years who receive biennial screening mammography to meet the HP2030 target of 80.3%
    - Increase the proportion of men ages 55 to 69 years that discuss the possible benefits and harms of prostate-specific antigen (PSA) screening with their health care provider and make an individualized decision about whether to get screened
- **Adoption**
  - Percentage of providers who receive education on screening guidelines for breast, lung, and prostate cancer
  - Uptake of cancer screening in the field by number of providers

- Percentage of provider staff that engaged with navigation program
- **Implementation**
  - Number of patients referred to navigation program
  - Rates of 1) low dose CT lung cancer screens 2) biennial screening mammography, and 3) prostate specific antigen (PSA)
  - For those who have a positive screen: 1) time to referral, 2) time and barriers/facilitators to diagnosis 3) uptake of treatment, and 4) number screened for clinical trials
- **Maintenance**
  - Measure of primary outcomes at 3 months post-intervention with progress towards Healthy People 2030 goals
  - Short-term attrition rate
  - Differential rates by patient characteristics

Medical records will be followed until definitive diagnosis and treatment disposition to track the patients' progress through the cancer care continuum. If diagnosis is negative, then interaction with the medical record ends upon confirmation of negative test. If diagnosis is positive, then the medical record is followed monthly to determine: diagnostic codes, treatment decisions, treatment course, and treatment outcomes. This may include labs, demographics, medication histories, referrals, outpatient visit notes, inpatient progress notes, and imaging.

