#### Recruitment of Patients

Patients undergoing screening as standard of care will have access to clinic-based educational materials, i.e. signage and pamphlets in English and Spanish on cancer screening, diagnosis and care and on the study opportunity.

As standard of care for patients who screen positive, a care navigator will be assigned. The care navigator will provide patients with study recruitment materials and information, ensuring patients are aware that study involvement does not impact care navigation or treatment.

After positive breast, lung, and/or prostate cancer screening in the field or at an emergency room or care facility, study team members will be informed of positive field screens. Patients with positive screens will be referred for confirmatory diagnostic testing and will receive guidance from care navigator and the financial navigator to set up appointments. A study team member will meet the potential participant at the site of diagnostic testing and/or at emergency departments or other urgent care sites to introduce the study and obtain informed consent for research activities.

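### The first Effectiveness measure, referral of positive screens, records delivery of a prescribed step and cannot show whether navigation leads to diagnosis

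*Protocol*

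**What the plan says.** Under Study Outcome Measures, Dashboard and Records, the first Effectiveness entry is "All positive screens referred for confirmatory diagnostics". It has no numerator, denominator, baseline or comparator. The other Effectiveness entries are lung and breast screening rates against Healthy People 2030 targets and a goal on PSA discussions. Time to referral and time to diagnosis for positive screens are collected, but under Implementation.

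Recruitment of Patients makes the referral routine: "Patients with positive screens will be referred for confirmatory diagnostic testing". Consent Process places the approach to the patient after that step: "Upon referral for definitive diagnosis based on their cancer screening results, patients will be contacted by a study team member for informed consent". The entry condition itself is only the positive screen: "Receives a positive screening result for lung, breast, and/or prostate cancer at a study site".

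Research Design sorts these measures differently. There, Effectiveness is monthly screening referral uptake compared with baseline, and the count of positive-screen patients referred onward (the text says for screening and for treatment) belongs to Adoption. Primary Objective Analysis assigns barriers data and patient-reported outcomes to Effectiveness, describes referral data by percent change, and assigns fidelity to Implementation.

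The Background hypothesis includes prompt definitive diagnosis as a result of navigation, and the primary objective names diagnosis alongside screening and treatment.

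**The concern.** An Effectiveness measure should be able to come out badly if the programme does not work. This one records whether staff carried out a step that the protocol tells them to carry out. In consented patients the step comes before entry, so the result is settled before any observation begins. Over all positives it can vary, but only with staff compliance.

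What navigation is meant to change comes after the referral: whether the patient attends, is diagnosed, and how soon. The secondary objectives plan to compare people who accept follow-up diagnosis with people who decline it, so loss after referral is expected. The referral measure cannot see that loss. A programme in which most referred patients never completed a work-up could still report full success on its first Effectiveness line. Describing percent change across the intervention adds little for a measure at or near its ceiling.

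**Working it through.** The protocol gives no rate, power or precision figure for this measure, so there is none to reproduce. The check is logical, with arithmetic to show size.

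**Inputs.** Planned subjects: 200 (Study Site(s)/Location(s) and Number of Subjects). True referral rate r among positive screens: not given; assumed 50% to 100%. Diagnostic completion c after referral: not given; assumed 40% and 90%. Every referred patient is taken to consent, for simplicity.

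**Step 1: two possible denominators.**
- Consented patients. Consent is sought upon referral, so every consented patient has been referred. Proportion = 200/200 = 100% for any r.
- All positive screens. Enrolling 200 requires 200/r positives, and the proportion is 200 ÷ (200/r) = r.

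| Assumed r | Positives, 200/r | Not referred | Consented cohort | All positives | Chance that all of 200 positives are referred, r^200 |
|---|---|---|---|---|---|
| 0.50 | 400 | 200 | 100% | 50% | 6 × 10^-61 |
| 0.90 | 222 | 22 | 100% | 90% | 7 × 10^-10 |
| 0.95 | 211 | 11 | 100% | 95% | 3.5 × 10^-5 |
| 0.99 | 202 | 2 | 100% | 99% | 0.13 |
| 1.00 | 200 | 0 | 100% | 100% | 1 |

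The last column treats referrals as independent. It shows that a complete score over all positives is not guaranteed.

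**Step 2: apparent precision.** For 200 of 200 the exact 95% lower limit is 0.025^(1/200) = 98.2%. In the consented cohort that limit would only reflect the order of referral and consent.

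**Step 3: sensitivity to what navigation should change.** With 200 consented patients, c = 40% gives 0.40 × 200 = 80 diagnosed and c = 90% gives 0.90 × 200 = 180. The two programmes differ by 100 patients; the referral measure reads 100% for both.

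**Step 4: where the protocol files the measure.**

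| Section | Referral of positives | Effectiveness |
|---|---|---|
| Research Design | Adoption | Screening referral uptake against baseline |
| Dashboard and Records | Effectiveness (time to referral: Implementation) | Referral of positives, screening rates, PSA discussion |
| Primary Objective Analysis | Referral data described by percent change | Barriers and patient-reported outcomes |

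The headings do not agree, and none of the three Effectiveness definitions includes completed diagnosis.

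**Step 5: follow-up available for a replacement.** The Study Duration list has enrolment through month 10 and final data collection in month 11 (its chart marks the final collection in month 12). With a 90-day window, taken only as an illustration of about 3 months, and a close at the end of month 11, full follow-up exists for positives up to about the end of month 8 (11 − 3). Later positives are cut off.

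**The case against.** The strongest reply is that the measure is worded over positive screens, not participants. It sits on a project dashboard that also describes non-participants, the team hears of positive field screens before consent, and referral is not an inclusion criterion. An instruction to refer can also fail across 20 sites, and the protocol measures time to referral as something that varies. All of this stands. A reader might infer that the measure is met by construction whatever the denominator. The documents do not support that: over all positives it equals the true referral rate.

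The reply does not rescue it as an Effectiveness measure. Even with that denominator it shows delivery of a prescribed step. The denominator is also not secure: record access to monitor outcomes is obtained through consent, and the waivers of consent and of HIPAA authorization are marked not applicable. If only consented data can be used, the result is fixed at 100%.

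A second reply is that other Effectiveness measures exist and that time to diagnosis and treatment uptake are collected, so poor diagnostic completion would not be hidden. This limits the consequence. It does not alter the fact that no Effectiveness item bears on the diagnosis part of the hypothesis.

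A reader might also infer that "Number of patients referred to navigation program" has the same fault, because the protocol says "As standard of care for patients who screen positive, a care navigator will be assigned". It does not: that entry is a volume count with no percentage ceiling, and it is already under Implementation.

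Finally, a completion measure has problems of its own. The protocol says "A study team member will meet the potential participant at the site of diagnostic testing and/or at emergency departments or other urgent care sites", so some patients may consent when they have already attended, and late positives have short follow-up. Both points are right and must be dealt with in the fix.

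**Conclusion.** The concern holds in a limited form. Referral of positive screens is a fidelity measure placed under Effectiveness. It is exactly 100% in consented patients (200/200, whatever the true referral rate). Over all positives it equals the referral rate, which the prescribed procedure should keep near the ceiling; that is an expectation, since the protocol gives no rate. In neither case does it tell 40% diagnostic completion from 90%. The sections also conflict on what Effectiveness means and on where referral of positives belongs.

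The first conclusion rests on consent following referral, as Consent Process states. The completion and referral rates used here are illustrative. The measure carries no hypothesis test and is not the only Effectiveness item, so this is a correction that should be made; it does not undermine the study as a whole.

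**What to change.** In Dashboard and Records:

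- Move referral of positives to Implementation as a fidelity check, with the denominator stated as all positive screens at study sites, as an aggregate count. Reconcile this with the Adoption and Effectiveness definitions in Research Design.
- Add to Effectiveness the cumulative proportion of positive screens with a completed confirmatory diagnosis by a prespecified time from the positive result, and place time to diagnosis beside it.
- Count decliners and non-attenders as not completed. Treat patients whose window is cut off by the month-11 data close as censored, or limit the fixed-window proportion to positives with full follow-up.
- State the denominator and data source: all positives if aggregate or authorised data allow, otherwise consented patients. In the latter case report those consented at the diagnostic testing site separately, because they have already attended.

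For consented patients the cost is mostly wording and a dashboard metric, since time to diagnosis and record follow-up to diagnosis are already planned. Covering all positives needs a stated basis for data on people who did not consent. The reported figure will fall below 100%, and late enrollees will contribute only partial follow-up.
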